## 3.5 Stopping Rule, IDMC, and Unblinding

There are no pre-specified stopping rules for the study. As discussed in more detail in Section 2.5 above, there is an IDMC for the ATHENA study, which will provide recommendations about the continuation, revision, or termination of the study. Additional details regarding the IDMC will be documented in a separate IDMC charter.

The patient, investigator, and study staff will be blinded to the patients' tumor HRD status and identity of the assigned treatment from the time of randomization until blind break of the ATHENA-COMBO comparison. Prior to enrollment, the investigator will receive tissue BRCA mutation results for patients in order to make an informed decision prior to enrolling patients into this study considering the approval of PARPi in current patient populations in certain countries. If an individual's role on the trial requires information about HRD status or treatment assignment (eg, an individual is involved in emergency unblinding or entry of HRD status for stratification), procedures will be used to ensure all other personnel remain

Confidential 21 of 52

blinded. Study treatment assignment will be available to the investigator upon request for post-study treatment planning.

The sponsor study team was unblinded to study arm B (rucaparib + IV placebo) and arm D (oral placebo and IV placebo) on 23 March 2022 when the ATHENA-MONO primary analysis was performed but remained blinded to study arms A (rucaparib + nivolumab) and C (oral placebo + nivolumab). A separate blinding plan has been implemented for ATHENA outlining the details of the blinding process and is used for training with all study personnel and sponsors.

Confidential 22 of 52

## 4 PATIENT DISPOSITION

The following patient disposition will be summarized by treatment arm:

- Number of patients in each analysis population;
- Number of patients that have discontinued oral study drug and the primary reason for discontinuation, for all patients and broken out by those that continued treatment postradiological progression and those who did not continue treatment post-radiological progression;
- Number of patients that have discontinued IV study drug and the primary reason for discontinuation;
- Number of patients by end-of-treatment status of both Oral and IV study drug; Study drug never initiated, Study drug never initiated due to COVID-19, Study drug discontinued, and Study drug completed; and.
- Number of patients by the end of study status; discontinued treatment for oral and IV study drug, withdrew consent, lost to follow-up, death, and still in active long-term follow-up (ie, discontinued both oral and IV treatment, but are still being actively followed for post-progression endpoints and overall survival).

## 4.1 Disposition and Summary of COVID-19 Impact

The number of patients who were ongoing and impacted by COVID-19 will be summarized. This is defined as all patients ongoing, or in Long-term Follow-up starting with visits dated on and after 01 February 2020. The number of tumor scans missed, visits missed, and the number of telehealth visits will also be summarized for both the ITT Population and the Safety Population.

#### 5 PROTOCOL DEVIATIONS

Major protocol deviations will be identified prior to releasing the treatment codes for the primary efficacy analysis in accordance with pharma& SOP8223 (Protocol Deviations Management). A listing with all the major protocol deviations will be presented. No patients will be excluded from the efficacy population due to a major protocol violation.

#### 6 DEMOGRAPHICS AND BASELINE CHARACTERISTICS

All demographic and baseline characteristics will be summarized by treatment group and overall for the ITT and Safety Populations. Additional analyses for the PD-L1 (IC  $\geq$ 5% and IC  $\geq$ 1%) and HRD stratification (ie, tBRCA, non-tBRCA LOHhigh, non-tBRCA LOHlow, and non-tBRCA LOHunknown) subgroups may also be performed.

## 6.1 Demographics

The demographic variables will be summarized with frequency tabulations that will focus on identifying differences between treatment groups in the extreme values of the distributions.

Confidential 23 of 52

Descriptive statistics may also be used to summarize the quantitative variables. The demographic variables presented will include age, height, weight, gender, race, ECOG performance status, and geographic region using the following categorizations:

- Age (years):  $\leq 50$ , 51-60, 61-70, 71-80, 81-90,  $\geq 90$ ; and  $\leq 65$ , 64-74,  $\geq 75$ ;
- Height (cm):  $\leq 75$ , > 75-100, > 100-125, > 125-150, > 150-175, > 175;
- Weight (kg):  $\leq 50$ , > 50-75, > 75-100, > 100-125, > 125-150, > 150;
- Gender: Female;
- Race: American Indian or Alaska Native, Asian, Black or African American, Native Hawaiian or Other Pacific Islander, White, Multiple, Other, or Not Reported;
- Ethnicity: Hispanic or Latino, Not Hispanic or Latino, Unknown, or Not Reported;
- ECOG performance status: 0, 1;
- Smoking status: Current smoker, Former smoker, never smoked;
- Country; and
- Geographic region (United States/Canada, Western Europe, Eastern Europe, Latin America, Asia/Africa/Oceania).

These categorizations may be adjusted if the majority of the data lies in only 2 or 3 of the categories.

# 6.2 Cancer History and Prior Anticancer Treatment, and Disease Burden at Randomization

## 6.2.1 Cancer History and Prior Anticancer Treatment and Surgery

A summary table on the baseline clinical characteristics across patients by treatment and overall will be summarized according to the following:

- Time since diagnosis (months): 0 to 3, > 3 to 6, > 6 to 9, > 9 to 12, > 12;
- Type of ovarian cancer (ie, Epithelial, Primary Peritoneal, Fallopian Tube);
- Cancer histology and stage at enrollment;
- Number of prior chemotherapy regimens, and platinum-based regimen;
- Number of cycles of prior chemotherapy regimen, and platinum-based agent;
- Number of patients by administrative setting of front-line regimen (IV only with HIPEC, IV only without HIPEC, IP only with HIPEC, IP only without HIPEC, IV and IP with HIPEC, IV and IP without HIPEC);
- Number of patients with prior bevacizumab use;
- Duration between randomization and the date of first day on the last dose of chemotherapy (in weeks);
- Randomization stratification of disease status (no residual disease vs residual disease);
- Disease status (no residual disease vs residual disease) based on EDC data;

Confidential 24 of 52

- Randomization stratification of timing of surgery (primary surgery vs interval debulking);
- Timing of surgery (primary surgery vs interval debulking) based on EDC data;
- Best radiological response to front-line treatment (CR, PR, No Disease post-surgery, Inevaluable, or Other);
- Best GCIG CA-125 Response to front-line treatment (Response, No Response, Inevaluable, Other);
- Disease Free with normal CA-125 defined as Best radiological response (CR, No Disease Post-surgery) and CA-125 ≤ ULN (Yes, No)
- Number of prior surgeries (0, 1, 2, > 2);
- Type of surgery (BSO, hysterectomy, partial omentectomy, and full omentectomy and Other); and
- Cytoreductive Surgery Outcome (Complete Resection=R0, microscopic residual < 1 cm, Macroscopic residual ≥1 cm, Not applicable).

Descriptive statistics may also be used to summarize these variables.

#### 6.2.2 Disease Burden at Randomization

A summary table on the disease burden characteristics across patients by treatment and overall will be summarized according to the following:

- Patients with measurable disease by investigator (ie, target lesions identified by RECIST v1.1);
- Patients with non-measurable disease by investigator (ie, non-target lesions only identified by RECIST v1.1);
- Patients without any disease by investigator (ie, no target lesions and no non-target lesions identified by RECIST v1.1); and
- Number of patients with CA-125 values within normal limits at baseline based on central laboratory results.

## 6.3 PD-L1 Expression, HRD Classification and BRCA Results

A summary table of the PD-L1 expression, HRD classification and BRCA test results by treatment and overall will be presented. The PD-L1 expression is based on the archival tumor tissue or a screening biopsy tested by CellCarta. The HRD classification is based on the archival tumor tissue or a screening biopsy tested by FMI. In addition, blood samples will also be collected and tested by an external central laboratory for any germline BRCA mutation. The patients may also have had local BRCA testing with the result entered in the eCRF during Screening. The following test results will be summarized:

- PD-L1 expression utilizing a 5% IC cut-off and a 1% IC cut-off
- The randomization stratification variables from FMI:

Confidential 25 of 52

- HRD classification (tBRCA, non-tBRCA LOHhigh, non-tBRCA LOHlow, or non-tBRCA LOHunknown) by central laboratory analysis;
- BRCA by local testing (BRCA1, BRCA2, or not detected);
- BRCA by central blood testing (BRCA1, BRCA2, or not detected);
- Overall BRCA status from local and central (BRCA1, BRCA2, or not detected);
   and
- Overall Germline/Somatic status (see Table 3 below for categories).

The tumor tissue-based assay used in this study identifies sequence variants in the BRCA1 and BRCA2 genes; however, it does not distinguish between the mutation type of germline or somatic. In order to further explore the mutation type, data from local BRCA test and/or a central blood test of germline BRCA will be used to derive the mutation type according to Table 3 below.

Table 3 Algorithm for Determination of Germline/Somatic Status

CTA Result	Germline Blood Test Result (central a and/or local test b result c )	Designation
BRCA-positive	BRCA-positive	Germline
BRCA-negative	BRCA-positive	Germline
BRCA-positive	BRCA-negative	Somatic
BRCA-positive	Not tested	Unknown

- a. Blood sample
- b. Blood or buccal sample
- c. If either the central or local test is BRCA-positive then the patient is considered BRCA-positive

## 6.4 Medical History

The medical history will be summarized for the Safety Population. Medical history events will be classified using the MedDRA classification system version 25.0 or higher. Medical history data will be summarized using frequency tabulations by SOC and PT.

## 7 STUDY DRUG EXPOSURE AND COMPLIANCE

## 7.1 Extent of Exposure

Analyses in this section will be performed in all treated subjects by treatment group as treated. Listings will include all available exposure data.

Table 4 summarizes the key parameters used to calculate exposure.

Confidential 26 of 52

## Table 4 Key Parameters used to Calculate Exposure

#### Administration of study therapy: definition of parameters

	Rucaparib	Nivolumab
Dosing schedule per protocol	600 mg BID	480 mg every 4 weeks
Dose	Dose (mg) is defined as Total Dose administered. Dose administered in mg at each dosing date are collected on the eCRF.	Dose (mg) is defined as Total Dose administered. Dose administered in mg at each dosing date are collected on the eCRF.
Relative dose intensity (%)	Time normalized actual dose received /600 mg BID	[Cumulative dose (mg) / ( (Last dose date – first dose date + 28) $\times$ 480/28)] $\times$ 100
Duration of treatment	Last dose date - Start dose date +1	Last dose date - Start dose date +1

Oral and IV study drug exposure will be summarized for all patients in the Safety Population. At the time of the visit cut-off, all patients will have discontinued treatment for protocol-specified reasons or because they reached the treatment cap of 24 months for treatment with the oral/IV combination. The duration will be summarized with summary statistics and by categories (0 to 6 months,  $\geq$  6 to 12 months,  $\geq$  12 to 24 months,  $\geq$  24 months) for each treatment arm.

For oral study drug, the number of patients with at least 1 dose reduction due to a TEAE based on the dosing log will be summarized with frequencies and percentages. Any dose reduction regardless of duration will be summarized. In addition, protocol-specified dose reductions will be broken up by dose level and by reason (ie, AE, non-compliance, or other). That is, the number of patients on each protocol-specified oral dose level will be summarized (ie, 600 mg BID, 500 mg BID, 400 mg BID, 300 mg BID, etc.) in order to assess patients with multiple levels of oral dose reductions. Dose reduction is defined as 3 or more consecutive days at that protocol-specified dose level. The number of patients with at least 1 dose re-escalation will be summarized for each protocol-specified oral dose level from which they escalated.

The number of IV cycles given per treatment arm will also be summarized.

The following parameters will also be summarized for IV study drug:

- Cumulative dose (sum of the doses administered per patient) and infusion duration (stop time start time for each infusion).
- Dose delays: number of patients with at least 1 delay, number of delays per patient, reasons for delays, and length of delays.

Confidential 27 of 52

• Infusion interruptions: number of patients with at least 1 interruption, number of interruptions per patient, and reasons for interruptions.

#### 8 CONCOMITANT MEDICATIONS

Concomitant medications to oral or IV study drug will be summarized for all patients in the Safety Population. All treatments taken concomitantly with oral or IV study drug will be summarized in frequency tabulations for each randomized treatment group and overall. All treatments will be coded utilizing the WHO Drug Dictionary version 202103 (WHODrug-Global-B3) or later.

Concomitant to oral or IV study drug is defined as all treatments that are either ongoing at the date of the first oral or IV dose or are started prior to the end of the treatment-emergent window (ie, within 28 days of date of last dose of oral study drug or within 5 months of the last dose of IV study drug). A listing of all concomitant treatments will be provided. In addition, a listing of all treatments that are deemed either prior to or post oral or IV treatment will be included in a separate listing. If either the start date and/or the stop date of the medication is missing so that it is unclear whether the medication was stopped prior to first dose of oral or IV study drug, then that medication will be classified as concomitant to oral or IV study drug.

#### 9 EFFICACY VARIABLES

## 9.1 Primary Efficacy Variable

The primary efficacy variable is investigator determined PFS (invPFS).

## 9.2 Secondary Efficacy Variables Included in the Step Down Analysis

- OS
- ORR by RECIST v1.1 in patients with measurable disease at baseline

# 9.3 Secondary Efficacy Variables Not Included in the Step Down Analysis

- BicrPFS
- DOR by RECIST v1.1 in patients with measurable disease at baseline

## 9.4 Exploratory Efficacy Variables

- PFS of study treatment followed by the subsequent line of treatment (PFS2), defined as the time from randomization to the second event of disease progression or death, as assessed by the investigator
- To evaluate the contribution of nivolumab monotherapy vs placebo (invPFS, bicrPFS, OS, ORR, DOR, and safety)

Confidential 28 of 52

- To evaluate the contribution of combination rucaparib + nivolumab vs nivolumab (invPFS, bicrPFS, OS, ORR, DOR, and safety)
- To evaluate the contribution of combination rucaparib + nivolumab vs placebo (invPFS, bicrPFS, OS, ORR, DOR, and safety)
- To evaluate efficacy in HRD subgroups (tBRCA, non-tBRCA LOHhigh, non-tBRCA LOHlow, non-tBRCA LOHunknown, and HRD (tBRCA + non-tBRCA LOHhigh) for the comparison of rucaparib + nivolumab vs rucaparib
- Health-related Quality of Life (HRQoL) as assessed by the trial outcome index (TOI) of the Functional Assessment of Cancer Therapy Ovarian (FACT-O)
- Patient-reported outcome (PRO) utilizing the Euro-Quality of Life 5D (EQ-5D)
- Mutations in non-tBRCA HRR genes as a molecular marker of efficacy
- PD-L1 expression and TMB as molecular markers of efficacy
- Variants in circulating tumor DNA (ctDNA) as markers of response and resistance
- PK of rucaparib as monotherapy and in combination with nivolumab
- PK of nivolumab as a monotherapy and in combination with rucaparib
- Immunogenicity of nivolumab when administered as a monotherapy and in combination with rucaparib
- Exposure-response relationship between selected exposure measures of rucaparib and nivolumab, and safety and efficacy endpoints

Confidential 29 of 52

### 10 EFFICACY ANALYSIS

## 10.1 Primary Efficacy Analysis

The primary efficacy endpoint is PFS as assessed by the investigator (invPFS). The time to invPFS will be calculated in months as the time from randomization to disease progression +1 day, as determined by RECIST v1.1 criteria or death due to any cause, whichever occurs first. Only scans or deaths prior to and on the start of any subsequent anticancer treatment will be used in PFS analysis. Any deaths or progression events occurring within 2 missing expected scan assessments will be included in the analysis. Two missed scans or visits is defined as a duration of 26 weeks (12 x 2+2) for the first 3 years and 50 weeks (24 x 2+2) thereafter. Events occurring immediately after 2 consecutive missed scans will be censored as below.

Censoring rule: Any patients who do not experience an event of either disease progression or death will be censored on the last on-study tumor assessment prior to start of any subsequent anticancer treatment. Any patient with an event of either disease progression or death following 2 or more missed expected consecutive scans will be censored on the date of the last on-study tumor assessment prior to the gap in scan collection. If a patient has an evaluable non-PD scan immediately following the gap, the gap-clock will reset and subsequent scans and events (progression or death) may be used in the primary PFS assessment (barring intervening SACT, as above). If a patient does not have any on-study tumor assessments, then the patient will be censored on the date of randomization (ie, Day 1).

The overall tumor assessment date for visits where multiple scans were utilized to make the assessment will be based on the following rule: the scan date showing the disease progression will be used for events where there is disease progression. For censored patients, the later date of the tumor scans within the assessment will be used.

The randomization stratification factors included in the primary analysis of invPFS are:

- HRD classification (tBRCA, non-tBRCA LOHhigh, non-tBRCA LOHlow, or non-tBRCA LOHunknown) by central laboratory analysis;
- Disease status post-chemotherapy (residual disease vs no residual disease); and
- Timing of surgery (primary surgery vs interval debulking).

The primary endpoint will be tested using a stratified log-rank test of invPFS between the randomized treatment groups and will be considered the official test used for the hierarchical testing outlined in Section 3.4.

A graphical presentation of unstratified invPFS distributions, median invPFS with 95% CI, and event rates will be presented as supportive statistics. Furthermore, the probability of being progression free at 6, 12, 18 and 24 months will be summarized by treatment group using the Kaplan-Meier estimates, both unstratified and stratified, at each time point with 95% CIs using a log-log distribution.

Confidential 30 of 52

Additionally, the primary endpoint will be analyzed using the stratified Cox proportional hazard methodology, presenting the hazard ratio with 95% confidence interval between the randomized treatment groups.

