Patients will be assessed for disease status per RECIST v1.1 every 12 calendar weeks (flexibility with scheduling within 1 week prior to planned imaging date is permitted) relative to C2D1 (the first scan will be 16 weeks after initiation of oral study treatment) for the first 3 years and every 24 weeks thereafter until objective radiological disease progression; disease status will also be assessed at discontinuation of treatment and as clinically indicated. Disease progression will only be determined by RECIST v1.1 (Section 7.5.3.1). Patients with a CR at study entry will only be considered to have disease progression if a new lesion is identified based on guidelines outlined in RECIST v1.1. Patients who meet GCIG CA-125 criteria for disease progression should have a radiologic assessment and be assessed by RECIST v1.1. If the radiologic assessment does not confirm disease progression, patients should continue on treatment and be assessed by RECIST v1.1 per the protocol schedule of assessments. Patients experiencing disease progression by RECIST v1.1, as assessed by the investigator, will be discontinued from treatment and enter follow-up. If the patient has met criteria for radiologic progression by RECIST, but the patient is still receiving benefit from the study drug(s) (eg, patient has mixed radiologic response or is continuing to have symptomatic benefit), according to the investigator, then continuation of treatment will be considered for a maximum cumulative duration of 24 months after initiation of oral/IV combination study treatment (see Section 5.13). Patients will continue to have all protocol-required assessments specified in the Schedule of Assessments (Table 5).

PRO assessment will occur on Day 1 of Cycles 1 through 3, Cycle 5, then every 12 weeks (aligning with tumor assessment scans) until treatment discontinuation or until the data cut-off for the primary endpoint analysis, whichever comes first.

All CT scans (and other imaging, as appropriate) performed during the treatment period and at treatment discontinuation will be collected for BICR.

Patients will be continuously monitored for safety. An IDMC with multidisciplinary representation will evaluate safety in compliance with a prospective charter.

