7.5.3 Efficacy Evaluations

7.5.3.1 Disease/ Tumor Assessments

Tumor assessment measurements will be performed at screening, at the end of every 12 weeks of treatment (up to 7 days prior permitted) relative to C2D1 for the first 3 years and every 24 weeks thereafter until objective radiological disease progression. If C2D1 visit did not occur, the first on-study scan should occur 16 weeks after C1D1. Tumor assessments should be performed at the time of treatment discontinuation if the reason for discontinuation was other than radiologically confirmed disease progression and it has been \geq 12 weeks since the last assessment. In addition, tumor assessments should be made as clinically indicated. Also see Section 6.8.

Disease assessment will comprise clinical examination and appropriate imaging techniques per RECIST v1.1 (CT and/or MRI scans of the chest, abdomen, and pelvis with appropriate slice thickness per RECIST). Other complementary studies (X-ray, PET, and ultrasound) may be performed if required. If a site can document that the CT performed as part of a

PET/CT is of identical diagnostic quality to a diagnostic CT (with IV and oral contrast) then the CT portion of the PET/CT can be used for RECIST measurements. All sites of disease should be followed, and the same methods used to detect lesions at baseline are to be used to follow the same lesions throughout the clinical study. The same methods used to detect lesions at baseline are to be used to follow the same lesions throughout the clinical study. CT/MRI scans of the chest, abdomen, and pelvis performed to determine the extent of disease at baseline should also be performed at each time of disease assessment, even if the scans were negative at baseline. Investigators should perform scans of other anatomical sites that, in their judgment, are appropriate to assess based on each patient's tumor status. Imaging guidelines provided by the BICR vendor and should be followed for the collection of images and the radiological assessment of disease.

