9.6 Efficacy Analyses

9.6.1 Primary Efficacy Analyses

The primary efficacy endpoint for the study is investigator-determined PFS (invPFS) by RECIST. Investigator-determined PFS is defined as the time from randomization to disease progression, according to RECIST v1.1 criteria as assessed by the investigator, or death due to any cause, whichever occurs first. Only scans or deaths prior to or on the start of any subsequent anticancer treatment will be used in PFS analysis. Any death or progression event

occurring within 2 missing expected scan assessments will be included in the analysis. Two missed scans or visits is defined as a duration of 26 weeks $(12 \times 2 + 2)$ for the first 3 years and 50 weeks $(24 \times 2 + 2)$ thereafter. Events occurring immediately after 2 consecutive missed scans will be censored as below.

Censoring rule: Any patients who do not experience an event of either disease progression or death will be censored on the last on-study tumor assessment prior to start of any subsequent anticancer treatment. Any patients with an event of either disease progression or death directly following 2 or more missing expected consecutive scans will be censored on the date of the last on-study tumor assessment prior to the gap in scan collection. If a patient does not have any on-study tumor assessments, then the patient will be censored on the date of randomization (ie, Day 1).

The stratification factors included in the primary analysis of invPFS will be as follows:

- HRD classification (tBRCA, non-tBRCA LOH^{high}, non-tBRCA LOH^{low}, or non-tBRCA LOH^{unknown}) by central laboratory analysis
- Disease status post-chemotherapy (residual disease vs. no residual disease)
- Timing of surgery (primary surgery vs. interval debulking)

The primary endpoint is analyzed using stratified Cox proportional hazard model and log-rank test comparing the treatment groups stratified by the randomization stratification factors, ie, HRD classification (tBRCA, non-tBRCA LOH^{high}, non-tBRCA LOH^{low}, and non-tBRCA LOH^{unknown}), disease status (no residual disease versus residual disease), and timing of surgery (primary surgery vs. interval debulking). The log-rank test will be the official test used for evaluating primary endpoint significance in the step-down procedure.

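### The primary invPFS rule contradicts itself for patients who die early with no on-study scan: one sentence counts the death, another censors it at Day 1

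*SAP*

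**What the plan says.** COMBO SAP 10.1 sets out the primary endpoint in these steps.

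- **Event.** Progression "as determined by RECIST v1.1 criteria or death due to any cause, whichever occurs first".
- **Inclusion.** "Any deaths or progression events occurring within 2 missing expected scan assessments will be included in the analysis". The window is given a length: "Two missed scans or visits is defined as a duration of 26 weeks (12 x 2+2) for the first 3 years". Protocol 9.6.1 has the same rule for any death or progression "occurring within 2 missing expected scan assessments will be included in the analysis".
- **Censoring without an event.** "Any patients who do not experience an event of either disease progression or death will be censored on the last on-study tumor assessment", before any new anticancer therapy.
- **Censoring of late events.** An event after two or more consecutive missed scans is censored at the last scan before the gap.
- **No scan at all.** "If a patient does not have any on-study tumor assessments, then the patient will be censored on the date of randomization (ie, Day 1".

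On timing, Protocol 3.1.3 says "the first scan will be 16 weeks after initiation of oral study treatment". Protocol 7.5.3.1 shows that on-study means after baseline: "If C2D1 visit did not occur, the first on-study scan should occur 16 weeks after C1D1".

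The no-scan sentence also appears in Protocol 9.6.1, in MONO SAP 10.1, and in the bicrPFS rules (COMBO SAP 10.2.1, Protocol 9.6.2.1, MONO SAP 10.2.1).

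**The concern.** The general censoring sentence is expressly limited to patients without an event. The no-scan sentence is not, and it comes after text about patients who do have events, so its position does not tie it to the event-free group. For a patient who dies early with no on-study scan, whoever programs the endpoint must choose which sentence prevails.

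The choice affects the primary p-value. It also affects what follows: invPFS gates OS and ORR (COMBO SAP 3.4), and the central-review analysis proceeds only if invPFS is significant (COMBO SAP 10.2.1). IV drug starts at Cycle 2 Day 1, so weeks 4 to 16 include the first nivolumab exposure. If Arm A had more early deaths, Day 1 censoring would work in its favour. The sponsor study team has been unblinded to Arm B, the COMBO control, since 23 March 2022 (COMBO SAP 3.5). A choice left to programming, or made after the blind is broken, would be open to the charge of being data-driven.

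**Working it through.** **Step 1: which sentence covers whom.** Take a patient with no on-study scan and no subsequent therapy. The first scan is due at week 16 (112 days) after oral drug starts. Treatment starts within 3 days of randomization (Protocol 3.1.2), so the scan is due by day 112 + 3 = 115 from randomization. The second is due at week 16 + 12 = 28. The window is 26 × 7 = 182 days.

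| Time of death | Scans missed | Inclusion sentence | No-scan sentence |
|---|---|---|---|
| Before week 16 | 0 | Event | Censored Day 1 |
| Weeks 16 to 26 | 1 | Event | Censored Day 1 |
| Weeks 26 to 28 | 1 | Unclear: 26 weeks have passed, second scan not yet due | Censored Day 1 |
| After week 28 | 2 or more | Not included | Censored Day 1 |

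The first two rows conflict. The third is undefined, because the plan does not say where the 26 weeks start when there is no scan. The last is consistent, as is a death after new therapy has started, which the plan does not use.

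**Step 2: the plan's own figure.** Inputs from COMBO SAP 2.4: 600 events, hazard ratio 0.725, 400:400, one-sided alpha 0.0125, stated power 90%.

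- Log-rank variance V = 600/4 = 150; √V = 12.25.
- Expected |z| = |ln 0.725| × 12.25 = 0.3216 × 12.25 = 3.94.
- Critical value 2.241; power = Φ(3.94 − 2.24) = 95.5%.

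The stated 90% is therefore conservative (90% needs 481 events by the same formula). That has no bearing on this point; only V is carried forward.

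**Step 3: effect of dropping early deaths.** With 1:1 allocation, an early death adds about +0.5 to O − E if in Arm A and −0.5 if in Arm B. Removing a deaths in A and b in B shifts O − E by −(a − b)/2. The change in log hazard ratio is that shift divided by V, and the change in z is the shift divided by √V. The counts are assumptions: 8 and 16 deaths are 1% and 2% of 800, split 3:1.

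| Dropped, A vs B | Shift in O − E | Hazard ratio, from 0.725 | Shift in z | One-sided p that would read as 0.0125 |
|---|---|---|---|---|
| 6 vs 2 | −2 | 0.725 × e^(−0.0133) = 0.715 | 2/12.25 = 0.163 | 1 − Φ(2.241 − 0.163) = 0.019 |
| 12 vs 4 | −4 | 0.725 × e^(−0.0267) = 0.706 | 4/12.25 = 0.327 | 1 − Φ(2.241 − 0.327) = 0.028 |
| Equal | 0 | 0.725 | 0 | 0.0125 |

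**Step 4: simulation.** 1,500 runs, exponential medians of 20 and 28 months, 24-month uniform accrual, cut at 600 events.

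| Early deaths, A vs B | Hazard ratio, deaths counted | Hazard ratio, censored Day 1 |
|---|---|---|
| 4 vs 4 | 0.717 | 0.713 |
| 8 vs 0 | 0.735 | 0.713 |
| 16 vs 0 | 0.759 | 0.715 |
| 0 vs 8 | 0.700 | 0.715 |

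The direction agrees with step 3. Loss of information is negligible: with 16 events lost (584 left), power falls from 95.5% to 95.0%. Only imbalance between the arms matters.

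**The case against.** The strongest reply is that the section should be read as a whole. Both earlier censoring rules send the patient back to a last scan, and the no-scan sentence supplies a date when there is none. On that reading it never reaches a patient whose death is already an event, and a death before week 16 counts. This reading is coherent and may be what was meant. However, the text does not state that order of precedence, and the opposite result follows from applying the last sentence as written.

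Other points limit the consequence, and they stand:

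- Week 16 is only the first scheduled scan. Imaging is also done when clinically indicated, after CA-125 progression, and at discontinuation if 12 weeks have passed since the last scan (Protocol 7.5.3.1). Patients relapsing fast are among the likeliest to have one.
- OS counts every death. The sensitivity analysis using all scans and data (COMBO SAP 10.1.1.2) does too. It also adds events after subsequent therapy, so it does not isolate this rule, and it does not set the primary p-value.
- Adverse events with a fatal outcome are tabulated by arm (COMBO SAP 11.1), and deaths in the first four weeks precede any nivolumab.
- At the design effect z is about 3.9, so a shift of 0.16 to 0.33 would not change the conclusion.

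A reader might infer that the plan removes every death before week 16 from the primary endpoint and so hides early fatal toxicity. The documents do not support that. Another sentence in the same section counts those deaths, some of these patients may have a scan, and the deaths are visible in OS, the sensitivity analysis and the safety tables.

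**Conclusion.** The contradiction is real and sits in the primary-endpoint rule. For a no-scan death inside 26 weeks, two sentences of one section give opposite results. What is established is the conflict, not that such deaths will be dropped.

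If they were dropped, the bias would favour the arm with more of them. Its size rests on assumed counts and an assumed 3:1 split, for which the documents give no source: z moves by about 0.16 (6 versus 2) or 0.33 (12 versus 4). That matters only for a result near the 0.0125 boundary, and a balanced split has little effect. The point is worth settling because the endpoint should follow its own event definition, and because the correction is cheap if made before the COMBO result is known.

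**What to change.** Before the COMBO blind is broken, replace the no-scan sentence in COMBO SAP 10.1 and 10.2.1 and Protocol 9.6.1 and 9.6.2.1 with:

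*A patient with no on-study tumor assessment who dies within 26 weeks of randomization, and on or before the start of any subsequent anticancer treatment, is an event on the date of death. All other patients with no on-study tumor assessment are censored on the date of randomization.*

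State also that the 26-week window runs from randomization when there is no on-study scan, which settles weeks 26 to 28. The second sentence keeps a censoring date for no-scan patients who die after the window or after new therapy. Report the number of no-scan deaths by arm.

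For ATHENA-MONO, do not rewrite the rule. Its invPFS was evaluated at the 23 March 2022 cutoff, Arms B and D are unblinded, and no further invPFS analysis is planned unless health authorities ask (MONO SAP 3.5). Report how no-scan deaths were handled there.

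The cost is a short text change in the SAP and protocol and a small programming change. Death dates are already collected. The COMBO SAP lists the PFS censoring detail among the Amendment 4 changes made at FDA request, so the new wording should be shared with the agency.
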